8.2 PARTICIPANT DISCONTINUATION/WITHDRAWAL FROM THE STUDY

Subjects may be withdrawn from the study at their own request or at the request of their legally acceptable representative, or in case of inadvertent enrollment.

Individuals enrolled in the study who become incidentally incarcerated after enrollment will be withdrawn from continued participation until they are no longer incarcerated.

Participants will not be replaced if they withdraw after initial enrollment, and the data will be collected and included in the analysis up to the time of withdrawal.

A patient who is inadvertently enrolled fails to meet eligibility criteria; subjects inadvertently enrolled will be withdrawn from the study and their data removed. They are not considered a subject of planned enrollment.

8.3 LOST TO FOLLOW-UP

Obtaining complete data is a high priority for this trial because missing data could compromise the validity of the entire study. A participant will be considered lost to follow-up if he or she fails to return for the 6-month follow-up visit and is unable to be contacted by the study site staff.

The following actions must be taken if a participant fails to appear for the 6-month follow-up visit:

- The site will attempt to contact the participant and reschedule the missed visit and counsel the participant on the importance of maintaining the assigned visit schedule and ascertain if the participant wishes to and/or should continue in the study.
- Before a participant is deemed lost to follow-up, the investigator or designee will make every effort to regain contact with the participant. These contact attempts should be documented in the participant's study file.
- Should the participant continue to be unreachable after several attempts, he or she will be considered to have withdrawn from the study with a primary reason of lost to follow-up.

We will capture deaths among participants lost to follow up using various mechanisms, including review of the medical record, contacting the legal next of kin, or the contact provided at the time of study enrollment. For patients who are lost to follow up, we will also contact the primary care physicians and safety net clinics to ascertain the participant's vital status. In addition, local obituaries and newspapers will be screened for potential identification of lost to follow-up study participants.

9 STUDY ASSESSMENTS AND PROCEDURES

9.1 EFFICACY ASSESSMENTS

The initial study intervention (randomization and placement of a study device [tracheal intubation]) will be performed under exception from informed consent since the event will occur in an emergency situation. At the first available opportunity, an attempt will be made to obtain written informed consent from the participant or the authorized representative to continue participation in the study. Subjects

who have been randomized will be identified within 24 hours of intervention (tracheal intubation), and an attempt to approach the patient or more likely their legally authorized representative will be made immediately upon identification. In some cases, it may be difficult to identify the LAR immediately, but every effort will be made to obtain informed consent within 72 hours of randomization. Throughout the patient's hospitalization, data will be collected continuously from the time of randomization until hospital discharge or death.

A summary of the clinical data variables and definitions are listed below:

Baseline variables

Demographics: Patient demographic characteristics include age in years on the day of hospital admission, gender, race, ethnicity, weight and height, and county/state of residence. Participants' address and contact information will be maintained separately from the case report form and the study datasets, and linked via the study ID number, to enable re-contacting the participants after hospital discharge.

Clinical variables

Intubation procedure: PVC-ETT patients will be treated according to usual care, while EVAC-PU-ETT patients will receive continuous subglottic suctioning until removal of the ETT. As per the manufacturer's recommendation, continuous low-pressure suction at -20 mm Hg will be applied to the suction port. Procedural details of the intubation procedures will be collected as part of standard pre-formed intubation procedure notes. These details include indication for tracheal intubation, ETT type and size, methods of preoxygenation, induction medication, and instruments used. To quantify difficulty with laryngoscopy and ETT insertion, we will record the number of laryngoscopy attempts, and use of gum-elastic bougie to guide insertion of the tube. Furthermore, immediate complications will be gathered including aspiration noted during laryngoscopy, pharyngeal and tracheal injury, and extent of oxygen desaturation.

ICU admission and stay: Patient characteristics recorded will be demographics, APACHE II score, main reason for ICU admission, presence of community acquired pneumonia at admission, and indication for mechanical ventilation. In addition, patients' history of and current comorbidities will be collected and summarized using the Charlson comorbidity index. Variables that will be collected to derive outcome measures are: date of hospital admission, date of ICU admission, date/time of tracheal intubation (=time of initiation of mechanical ventilation), date/time of tracheal extubation (=time of discontinuation of mechanical ventilation), date/time of reintubation(s) and subsequent extubation(s) (if applicable), date and time of tracheotomy (if applicable), start and end date of each respiratory antimicrobial cycle initiated within 6 hours of intubation and while on mechanical ventilation, date of ICU discharge, date of hospital discharge, and date of death.

Post-extubation laryngeal dysfunction: Lack of cuff leak prior to study ETT removal, post-extubation upper airway obstruction, as evidenced by stridor requiring treatment (racemic epinephrine, helium-oxygen gas mixture) or resulting in re-intubation within 24 hours, will be recorded by observation and/or review of the medical record.

Monitoring VAE/VAP events: Patients will be monitored in the ICU until extubation, discharge or death. All patients will be monitored for the occurrence of VAP (see Appendix I for CDC definition of ventilator associated events) during the ICU stay. Diagnosis and treatment of VAP are standardized and their identification will be left to the judgment of the primary physician in charge of the patient. We will record all VAP events diagnosed based on respiratory cultures, all bronchoscopically and invasive diagnostic tests for pneumonia performed, and events of clinical VAP criteria based on both CDC criteria and a based on a clinical diagnosis.

Patient monitoring: Vital signs and physiologic variables will be monitored hourly until ICU discharge. The amount, color, and frequency of suctioning of endotracheal aspirates will be recorded daily. Isolates and quantity of respiratory cultures, and antimicrobial administration for respiratory indication will be collected.

VAP bundles and concomitant treatments that affect VAP: 1) Semi-recumbent position by capturing head of bed position (% of time >30° as automatically recorded by electronic beds); 2) stress ulcer prophylaxis, enteral calorie intake; 3) performance of oral hygiene, 4) use of neuromuscular blocking agents; 5) documentation of cuff pressure and application of subglottic suctioning; 6) Daily sedation vacation and spontaneous breathing trial (SBT).

VAP Treatment: Initial antimicrobial therapy is directed by hospital-wide guidelines. Use of respiratory antimicrobials and their duration will be collected.

During the ICU stay we will also collect the daily SOFA. As a summary measure, we will compute the mean of the daily score during the ICU stay.

Hospital stay variables: After discharge from the ICU, patients will be followed to obtain information on safety, disposition and antimicrobial treatment for VAP.

6-month follow-up: All patients will be followed-up six months after randomization with a structured in-person interview to screen for the presence of and assess airway symptoms or persistent sequelae of laryngeal dysfunction (Appendix II).¹⁰⁶ Any need for consultation of a specialist for airway complaints will be recorded and information abstracted from the medical record if appropriate. The clinical medical records release form collected at the time of informed consent will allow access to the subject's outside medical record for data related to the breathing problem. Quality of life will be also assessed, as measured by the physical component summary and the mental component summary of the Medical

Outcomes Study 36 Item Short-Form (SF-36) General Health Survey (Appendix IV).^{120, 121} We will also assess cognitive function using a battery of tests assessing domains previously demonstrated to be potentially affected by periods of respiratory distress and validated in both normal aging and cognitively impaired populations.¹²⁵⁻¹²⁸ The core battery will consist of measures from the National Alzheimer Coordinating Center's Uniform Data Set (UDS – Appendix V):^{129, 130} 1) Montreal cognitive assessment (MoCA), a global cognitive screen which has been shown to be much more sensitive than the Mini Mental Status Examination; 2) Craft Story Recall (an analogue to the Logical Memory subtest of the Wechsler Memory Scale), measuring immediate and delayed verbal contextual recall; 3) Benton Complex Figure test, which measures executive function and visuospatial ability, as well as visuospatial recall; 4) Digit Span, a test of attention and working memory; 5) Trail Making, Parts A and B, measures of attention and divided attention/working memory; and 6) Semantic and phonemic verbal fluency test. The follow-up visit will take from 60 to 75 minutes to complete.

Adverse Events (AE) monitoring: Any device-related AE will be recorded and evaluated for intensity, seriousness, causality in relationship to the study ETT, and actions taken. In the case of a device-related AE, the subject will be treated by the primary physician or referred for care, as appropriate. Additional details on AE and serious AE reporting are detailed in the Human Subject Section.

Economic variables

Healthcare resource utilization data will be obtained through extracts of electronic health record information for specific service items (i.e., x-rays, respiratory cultures, use of antimicrobials, etc.). The institution's direct cost (not charge) for billable items will be obtained from financial records of the cases as the measure of the cost. The cost of the device itself will be taken from the institution's supply purchase price (with sensitivity analysis for public reports of the price). The main consequence/outcome variables include: quality of life dimensions in SF-36, their summarized preference-based utility score from the SF-6D, neurologic function score, and mortality. Differential cost and consequence outcomes will be calculated for each arm.

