
Safety. Safety endpoints include clinical measures intended to evaluate the direct effect of the device at the site of placement. To evaluate the effect of the ETT at the local level we will be assessing subjective and

objective measures of laryngeal anatomy and function, in addition to any device-related adverse events. We will record: 1) airway complications at the time of ETT insertion; 2) the presence of cuff leak test prior to study ETT removal; 3) stridor immediately after extubation; 4) requirement for stridor treatment (racemic epinephrine, helium-oxygen gas mixture); or 5) reintubation within 24 hours due to upper airway complications such as stridor or obstruction. Long-term safety will be assessed by ascertaining the persistence of airway sequelae six months after randomization using a standardized questionnaire via in-person interview. Data collected include the presence of persistent throat discomfort or pain, residual hoarseness, change in voice, and dyspnea.

VAE: The trial will use CDC-defined Ventilator-Associated Events (VAEs). The tiered CDC approach includes the identification of ventilator associated conditions (VACs) in the first step, the presence of fever or increased white blood count and the initiation of new antimicrobial in the second step (IVAC), and documentation of a respiratory source of infection in the third step (possible ventilator associated pneumonia - VAP).

Study Population:

An estimated 1,074 patients will be enrolled in the study. Those eligible to participate in the trial are adult patients (older than 18 years of age) requiring emergency endotracheal intubation in the ED or in the hospital for acute respiratory distress or failure resulting in the requirement for Intensive Care Unit (ICU) admission and mechanical ventilation.

Inclusion criteria

Subjects eligible to participate in the trial are adult patients (18 years of age or older) requiring emergency endotracheal intubation in the ED or in-hospital for acute respiratory distress or failure resulting in ICU admission and mechanical ventilation. For a patient to be enrolled in the trial, a study intubation kit containing the study ID number must have been used for the emergency intubation.

[figure not shown]
Exclusion criteria

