	The trial started enrolling at OHSU and 90 participants were randomized. These activities were conducted under the oversight of OHSU IRB. After closing enrollment at OHSU, the study will enroll participants at YNHH only. Study oversight will be transferred to Yale IRB, including review of all Community Consultation and Public Disclosure activities, and oversight for the Public Disclosure activities in the Portland area at the conclusion of the study. The projected total study duration is 5 years (2018-2023).
Participant Duration:	Participants will be monitored for occurrence of VAEs until extubation. An appropriate size and model matched replacement ETT will be kept at the bedside until successful extubation or ICU discharge.

Participants will be monitored for other endpoints during ICU and hospital discharge, and until 6 months after extubation. At 6 months post-randomization, study participants will be evaluated in person either at our research facility space or at their residence for airway evaluation and related disorders, quality of life and cognitive impairment.

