Secondary Endpoints	
Safety. Safety endpoints include clinical measures intended to evaluate the direct effect of the device at the site of placement. To evaluate the effect of the ETT at the local level we will be assessing subjective and objective measures of laryngeal anatomy and function, in addition to any device-related adverse events. We will record: 1) airway complications at the time of ETT insertion; 2) the presence of cuff leak test prior to study ETT removal, as indicated by a difference between the inspiratory tidal volume (measured before cuff deflation) and the expiratory tidal volume (measured after cuff deflation) of at least 10% or >110 mL; 3) stridor immediately after extubation; 4) requirement for stridor treatment (racemic epinephrine, helium-oxygen gas mixture); or 5) reintubation within 24 hours due to upper airway complications such as stridor or obstruction. Long-term safety will be assessed by ascertaining the persistence of airway sequelae six months after randomization using a standardized questionnaire via in-person interview. Data collected include the presence of persistent throat discomfort or pain, residual hoarseness, change in voice, and dyspnea.
 
The main secondary clinical efficacy endpoint will be the incidence of CDC defined Infection-Related Ventilator-Associated Complications (IVAC)

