
occurring during the ICU stay from enrollment until ICU discharge. An IVAC event is defined by a 14-day period, starting on the day of onset of worsening oxygenation. For this study, we will use the CDC proposed tiered approach algorithm that encompasses ventilator associated conditions (VAC), infection related ventilator-associated complication (IVAC), and possible VAP.
 
Step 1: VAC (≥1 required):
 
 1) Daily min FiO_2 increase ≥ 0.20 (20 points) for ≥ 2 days - OR 2) Daily min PEEP increase $\geq 3 \text{ cm H}_2\text{O}$ for ≥ 2 days (after two days of stable or decreasing daily minimum values) 
Step 2: IVAC:
 
 1) Temperature $>38.0^\circ\text{C}$ OR $<36.0^\circ\text{C}$ - OR 2) White blood cell count $\geq 12,000$ or $\leq 4,000 \text{ cells/mm}^3$ - AND 3) A new antimicrobial agent is started and is continued for ≥ 4 days. 
Step 3: Possible VAP:
 
Criterion #1: Positive cultures of one of the following specimens collected within $+\/- 2$ days of onset of VAC, meeting quantitative or semi-quantitative thresholds, without requirement for purulent respiratory secretions: 1) Endotracheal aspirate; 2) Bronchoalveolar lavage; 3) Protected specimen brush; 4) Lung tissue - OR
 
Criterion #2: Purulent respiratory secretions AND a positive culture of one of the following specimens (qualitative culture, or quantitative/semi-quantitative culture without sufficient growth to meet Criterion #1): 1) Sputum; 2) Endotracheal aspirate; 3) Bronchoalveolar lavage; 4) Lung tissue; 5) Protected specimen brush.
 
Other secondary endpoints related to VAP
 
 1) Incidence of ventilator-associated events (VAEs); 2) Respiratory antimicrobial use; 3) VAP risk using a "clinical" definition for interpretation of the study findings in the context of previous literature where clinical definitions were used; 4) Occurrence of early- versus late-onset IVAC and time to first IVAC event. Early-onset IVAC is defined as IVAC occurring within four days of tracheal intubation while late-onset VAP is defined as VAP occurring 5 days or later. 
Additional secondary clinical endpoints
 
 1) 28-day ventilator-free days; 2) Daily Sequential Organ Failure Assessment (SOFA) score; 3) Length of ICU and hospital stay; 4) In-hospital and 6-month mortality comparison between the two groups.

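### IVAC, the main secondary efficacy endpoint, counts any new antimicrobial, but the antimicrobial data specified for surveillance and outcome derivation cover respiratory courses only

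*Combined protocol and SAP*

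**What the plan says.** **Definition.** Section 4 names IVAC as the main secondary clinical efficacy endpoint. Step 2 requires a temperature or white-cell criterion and also this: "A new antimicrobial agent is started and is continued for" at least 4 days. No indication is specified. The Synopsis (Section 2.1) confirms the order of the tiers: "the initiation of new antimicrobial in the second step (IVAC), and documentation of a respiratory source of infection in the third step". Section 4 counts IVAC "occurring during the ICU stay from enrollment until ICU discharge".

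**Antimicrobial data.** Among the variables collected to derive outcomes, Section 9.1 lists the "start and end date of each respiratory antimicrobial cycle initiated within 6 hours of intubation and while on mechanical ventilation". Under patient monitoring it says that "antimicrobial administration for respiratory indication will be collected". Its VAP treatment paragraph collects use and duration of respiratory antimicrobials. The daily VAE/VAP surveillance block of the Schedule of Activities (Section 2.3) has one antimicrobial row, for respiratory agents.

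**End of surveillance.** The Synopsis says: "Participants will be monitored for occurrence of VAEs until extubation". Sections 5.1 and 9.1 give extubation, discharge or death. The next sentence of Section 9.1 says monitoring for VAP covers the ICU stay.

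**Early and late onset.** Section 4 lists early- versus late-onset IVAC as an endpoint and defines early onset by IVAC, but then says "late-onset VAP is defined as VAP occurring 5 days or later".

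**The concern.** IVAC is the trial's main test of whether the tube prevents infection, which is the mechanism proposed for the benefit in quality of life and cognition. A respiratory filter on the antimicrobial data applies a third-tier requirement to a second-tier endpoint. A patient with worsening oxygenation and fever who starts an agent recorded for a non-respiratory infection meets the written definition, but has no specified dated course from which the 4-day rule can be scored.

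The filter also affects blinding. Section 5.1 accepts that caregivers will see which tube was used and relies on rule-based, objective adjudication as protection. If a course enters the algorithm only when it is labelled respiratory, an unblinded caregiver's label becomes one of the algorithm's inputs. Section 9.1 adds to the tension by leaving identification of VAP to the treating physician's judgment.

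**Working it through.** The plan states no IVAC rate, effect size or power, so there is no figure to reproduce. The main check sets the passages side by side.

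1. **Indication.** Definition: any new agent (Section 4, Step 2). Data: respiratory only, in the Section 2.3 surveillance row and three times in Section 9.1. The data specified are narrower than the definition.

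2. **Wider sources.**
   - Note 12 to Section 2.3 codes the indication, including empiric use and non-respiratory infection.
   - Section 7.5 puts concomitant prescription medications in the eCRF.
   - Section 9.1 (economic variables) extracts antimicrobial use from the electronic record.
   - None of these states start and stop dates for non-respiratory courses, and none is tied to IVAC.

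3. **Timing of the dated variable.** A VAC needs two days of stable or decreasing daily minimum settings before the worsening. A course started in response to it therefore begins days after intubation. If the 6-hour limit and the ventilation condition must both hold, nearly all IVAC courses are excluded. If they describe two alternative sets of courses, those begun on the ventilator are included. The sentence does not say which is meant.

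4. **Window.** Section 4 runs to ICU discharge and the Synopsis to extubation. Sections 5.1 and 9.1 run to extubation, discharge or death, and Section 9.1 then says the ICU stay. The FiO2 and PEEP rows of Section 2.3 cover Day 1, Day 2 to extubation, and VAE events. VAC rests on ventilator settings, so few events could begin off the ventilator. What is left open is ventilation after reintubation.

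5. **Onset classes.** Read literally, an IVAC on day 7 that does not reach possible VAP is neither early nor late.

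**Scale, by assumption only.** Take n = 537 per arm (Section 10.2) and two-sided 5% (Section 10.4.3). Assume a true control IVAC rate r, a true relative risk of 0.5 (Section 3.2 cites 0.51 for VAP; carrying it over to IVAC is an assumption), and a share m of events missed equally in both arms. Then p0 = r(1 − m), p1 = 0.5·r(1 − m), p̄ = (p0 + p1)/2, and

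power = Φ{[(p0 − p1) − 1.96·√(2p̄(1 − p̄)/n)] / √[(p0(1 − p0) + p1(1 − p1))/n]}.

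For r = 0.10 and m = 0: (0.05 − 1.96 × 0.01607)/0.01600 = 1.156, so power is 0.88.

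| r | m = 0 | m = 0.2 | m = 0.4 |
|---|---|---|---|
| 0.05 | 0.58 | 0.48 | 0.38 |
| 0.10 | 0.88 | 0.79 | 0.66 |
| 0.20 | 0.996 | 0.98 | 0.93 |

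Equal loss leaves the ratio p1/p0 unchanged and costs precision. Unequal loss biases the ratio. With no true effect, r from 0.05 to 0.20 and 90% capture in the PVC-ETT arm, the chance of a false significant benefit is:
- 0.04 to 0.06 if EVAC-PU-ETT capture is 85%;
- 0.06 to 0.14 if it is 80%;
- 0.13 to 0.43 if it is 70%.

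The nominal chance in that direction is 0.025. Capture that differed the other way would work against EVAC-PU-ETT. The documents do not show which of these cases, if any, applies.

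**The case against.** The strongest reply is that the plan collects more than these lines suggest. Note 7 to Section 2.3 covers respiratory antimicrobials for the whole ICU stay. The ventilation condition in Section 9.1 governs when a course starts, so its end date after extubation is still recorded. Section 11.1.8.1 describes extensive automatic abstraction from the electronic record. Section 9.1 presents its variables as a summary, and Appendix I or the Manual of Procedures, neither of which is in the text reviewed, may hold the operative algorithm.

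Much of this stands. A reader might infer that antimicrobials are recorded only on the ventilator; note 7 rules that out. A reader might infer that ventilator days after reintubation are lost. But Section 9.1 records reintubations and later extubations and monitors physiologic variables hourly to ICU discharge, so loss is only one reading. The VAP wording for late onset looks like a slip, because the item itself is headed as IVAC, and not like a deliberate choice of a stricter tier.

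The reply does not remove the core mismatch. Where the plan says what is collected for surveillance and outcome derivation, it says respiratory each time. The wider sources show that full capture is feasible, not that it is planned for IVAC.

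**Conclusion.** The mismatch between the IVAC definition and the data specified to score it is real and should be corrected. So should the ambiguous 6-hour wording, the inconsistent end of surveillance and the mixed tiers for onset. Missed events and label-dependent classification are risks of following the plan as written.

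Two stronger conclusions are tempting and not supported. The documents do not establish that qualifying events are in fact lost, because wider data may be available. Nor do they show that labelling differs by arm, in which direction or by how much. Any spurious relative risk would only restate the labelling rates assumed for it. The power and error figures above rest wholly on assumed event rates, effect and capture.

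The point concerns a secondary endpoint without a stated power target. It does not alter the 6-month primary analyses.

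**What to change.** - **Sections 2.3 and 9.1 (outcome variables, patient monitoring, VAP treatment):** extract from the electronic record the start and stop dates of all new systemic antimicrobials, whatever the indication, across the Section 4 window. Correct the 6-hour wording.
- **IVAC derivation:** state that it is done by algorithm without indication labels. Keep the respiratory label for the separate endpoint of respiratory antimicrobial use.
- **Window:** reconcile Sections 2.1, 2.3, 5.1 and 9.1 with Section 4. State that daily minimum FiO2 and PEEP are used on all ventilated ICU days, including after reintubation.
- **Onset:** in Section 4, define late onset as IVAC on day 5 or later.

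The cost is protocol and SAP wording, a wider medication query and slightly more data cleaning; electronic extracts of antimicrobial use are already planned for the economic aim. The change removes the label filter only. Unblinded clinicians still decide whether to start and continue an antimicrobial, and that should be reported as a limitation of the IVAC definition.
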